18.5 Missing Date of Investigational Product

When the date of the last dose of investigational product is missing for a subject in the Safety Population, all efforts should be made to obtain the date from the investigator. If it is still missing after all efforts, then the last visit date when investigational product was returned will be used in the calculation of treatment duration.

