**Investigational product, dose, and mode of administration:**

The drug product is SHP640 (0.1% Dexamethasone and 0.6% PVP-I) Ophthalmic Suspension.

The placebo product is Placebo Ophthalmic Solution.

Subjects will instill 1 drop of investigational product in each eye 4 times daily (with a minimum of 2 hours between doses) for 7 days.

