2.1 General Study Design

SHP640-302 is a global, multi-center, randomized, double-masked, parallel group, placebo controlled study designed to demonstrate the safety and efficacy of SHP640 ophthalmic suspension compared to placebo in treating adenoviral conjunctivitis.

Once screening and baseline assessments are complete and subjects are confirmed eligible to enroll in the study, subjects will be randomized, and investigational product will be administered on the same day (Day 1). The first dose will be administered by site staff on Day 1, and thereafter subjects will administer 1 drop in each eye 4 times a day (QID) for 7 days. Additional visits will occur on Visit 2 (Day 3), Visit 3 (Day 6), Visit 4 (Day 8), and Visit 5 (Day 12). All follow-up procedures will be conducted at Visit 5 (Day 12). The study will last up to 15 days.

Figure 1 provides the study design.

Figure 1: SHP640-302 Study Design

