^g If a non-dilated fundus exam is not feasible, a dilated examination should be conducted. For each subject the exam should be conducted the same way (either non-dilated or dilated) at both Visit 1 and Visit 5 (or ET).

^h All assessments, randomization, and investigational product instillation on Day 1 must take place with sufficient time to allow all 4 Day 1 doses (with a minimum of 2 hours between doses).

ⁱ The investigational product bottle should be shaken well prior to use at each dosing. The first dose will be administered by site staff on Day 1, and thereafter subjects will administer 1 drop in each eye 4 times a day for 7 days.

^j Investigational product instillation should only be performed in-office if it is necessary.

^k Monitoring for adverse events will begin after informed consent is obtained. Information about AEs unresolved at the time of study exit (eg, resolution status, resolution date, treatment received for AE) and related information (eg, data from any assessments conducted to follow up on the status of unresolved AE) for a period of up to 14 days after subject exit may be collected by the Sponsor. Corneal AEs that are ongoing at the end of study visit should be followed up by the site until resolution or stabilization and all related information should be collected in the CRF.

^l This sample will be used for baseline HSV testing for all subjects. For subjects <2 months of age, testing will also be conducted using the same sample for chlamydia and gonorrhea detection.

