8. EXTENT OF EXPOSURE

Exposure to double-masked investigational product for the Safety Population will be summarized in terms of treatment duration, which is calculated as the number of days from the date of first dose of double-masked investigational product taken to the date of the last dose of double-masked investigational product taken, inclusively, and irrespective of any investigational product interruption(s). Descriptive statistics will be presented by treatment group and overall.

Listings of investigational product exposure and study drug withheld will be provided for all subjects in the Safety Population.

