18.2 Study Visits and Windows

CRF visits will be used in all summary tables and listings.

Study day will be calculated as follows:

- If the assessment date is on or after the date of first instillation:

Study day = assessment date – first dosing date + 1

- If the assessment date is before the date of first instillation:

Study day = assessment date – first dosing date

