18.6.2 Incomplete Stop Date

The following rules will be applied to impute the missing numerical fields. If the date of the last dose of investigational product is missing, then replace it with the last visit date. If the imputed stop date is before the start date (imputed or non-imputed start date), then the imputed stop date will be equal to the start date.

Missing day and month

- If the year of the incomplete stop date is the same as the year as of the date of the last dose of investigational product, then the day and month of the date of the last dose of investigational product will be assigned to the missing fields
- If the year of the incomplete stop date is before the year of the date of the last dose of investigational product, then 31 December will be assigned to the missing fields
- If the year of the incomplete stop date is after the year of the date of the last dose of investigational product, then 01 January will be assigned to the missing fields.

Missing month only

- The day will be treated as missing and both month and day will be replaced according to the above procedure.

Missing day only

- If the month and year of the incomplete stop date are the same as the month and year of the date of the last dose of investigational product, then the day of the date of the last dose of investigational product will be assigned to the missing day
- If either the year is before the year of the date of the last dose of investigational product or if both years are the same but the month is before the month of the date of the last dose of investigational product, then the last day of the month will be assigned to the missing day
- If either the year is after the year of the last dose of investigational product or if both years are the same but the month is after the month of the date of the last dose of investigational product, then the first day of the month will be assigned to the missing day.

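### SAP 18.5 sets an unrecoverable last-dose date to the product-return visit with no cap (8-9 or 12-14 days for a return at Visit 4 or a full-schedule Visit 5, against 7 planned), and SAP 18.6.2 replaces the same date by a different rule

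*SAP*

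**What the plan says.** SAP 8 defines treatment duration as "the number of days from the date of first dose of double-masked investigational product taken to the date of the last dose", counted inclusively and ignoring interruptions.

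If the last-dose date is missing, SAP 18.5 first requires every effort to obtain it from the investigator. If that fails, "then the last visit date when investigational product was returned will be used in the calculation of treatment duration".

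SAP 18.6.2, on incomplete medication stop dates, has its own substitute for the same date: "If the date of the last dose of investigational product is missing, then replace it with the last visit date".

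The regimen is stated in the Protocol Synopsis as "4 times daily (with a minimum of 2 hours between doses) for 7 days", and in SAP 2.1 as a first dose at the site on Day 1, after which "thereafter subjects will administer 1 drop in each eye 4 times a day (QID) for 7 days". The schedule in SAP 2.4 adds that Day 1 procedures "must take place with sufficient time to allow all 4 Day 1 doses". The same schedule has product collected at Visit 4 (Day 8, +1 day) and at Visit 5 (Day 12, +2 days). A footnote ties the Visit 5 collection to subjects who discontinue.

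**The concern.** A visit at which product is handed back is a poor stand-in for the last dose. Both scheduled collection visits fall after the planned dosing period. Protocol 7.1.2 tells subjects not to dose within 12 hours of a visit and not to dose on the morning of Visit 4. The schedule marks no instillation at Visit 4 or Visit 5. For a compliant completer the rule therefore yields a duration that the regimen cannot produce, and nothing in 18.5 limits it.

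The two sections also fill one missing date in two ways. SAP 9 classifies a medication started on treatment by whether it began on or before the last dose, but it does not say which substitute applies when that date is missing.

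At stake is the exposure summary, Table 14.3.8.1. SAP 17 keeps full safety reporting in the abbreviated study report, so this table will be read. A single Visit 5 imputation could set its maximum to 12-14 days, which would look like dosing well beyond the regimen.

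**Working it through.** **Inputs**

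- Planned dosing: 7 days (Protocol Synopsis; SAP 2.1). All four Day 1 doses must be possible (SAP 2.4), so the seven days are read as Day 1 to Day 7.
- Day count: "Study day = assessment date – first dosing date + 1" (SAP 18.2), so the first dose is on Day 1.
- Duration = last-dose day − first-dose day + 1 (SAP 8).
- Collection visits: Visit 4 on Day 8-9 and Visit 5 on Day 12-14 (SAP 2.4).

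**Planned figure.** 7 − 1 + 1 = 7 days, which matches the regimen.

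**Return day put in place of last-dose day (18.5), for a subject who dosed through Day 7**

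| Return | Imputed duration | Excess over 7 | Percent |
|---|---|---|---|
| Visit 4, Day 8 | 8 − 1 + 1 = 8 | 1 | 14% |
| Visit 4, Day 9 | 9 | 2 | 29% |
| Visit 5, Day 12 | 12 | 5 | 71% |
| Visit 5, Day 13 | 13 | 6 | 86% |
| Visit 5, Day 14 | 14 | 7 | 100% |

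**Early stoppers (illustration).** A subject who stops on Day 3 and returns product at an early-termination visit on Day 4 shows 4 days against a true 3. One who stops on Day 3 and returns product at a full-schedule Visit 5 shows 12-14 against 3. Product cannot be returned before the last dose is taken, so the error is never downward.

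**Gap between the two rules.** Take a completer who returns product at Visit 4 and attends Visit 5. Under 18.5 the last dose is on Day 8-9. Under 18.6.2 it is on Day 12-14. The smallest gap is 12 − 9 = 3 days and the largest is 14 − 8 = 6 days. For that subject, a medication started on Day 10 is concomitant under SAP 9 if the 18.6.2 date is used, and not concomitant if the 18.5 date is used.

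**Effect on an arm mean.** The documents give no count of missing dates, so the imputed share *m* is an assumption. With all other subjects at 7 days, the mean is 7 + *m* × (imputed duration − 7). For imputed durations from 8 to 14:

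- *m* = 2%: 7.02 to 7.14 days
- *m* = 5%: 7.05 to 7.35 days
- *m* = 10%: 7.10 to 7.70 days

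**With a cap at Day 7.** The imputed last-dose day becomes the smaller of the return day and 7. Returns at Visit 4 or a full-schedule Visit 5 give 7 days, and the Day 4 early-termination return still gives 4. The Day 3 stopper who returns product at Visit 5 shows 7 rather than 12-14. The overstatement falls from 9-11 days to 4 but does not vanish.

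**The case against.** One can say in the plan's favor that the rule is a last resort and that little depends on it. Much of that stands. The rule operates only after a failed query. Treatment-emergent status in SAP 11.1 depends on the first dose, with no last-dose cutoff. The adverse-event tables give counts and percentages of subjects rather than exposure-adjusted rates. No efficacy summary uses the last-dose date. Medications are only listed, with imputed dates marked.

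One can add that the two rules serve different outputs: 18.5 feeds treatment duration, and 18.6.2 supplies a reference date for partial medication stop dates. That also stands, so this is one derived date left unreconciled, not two rules competing for one table. For medications begun before treatment, concomitant status turns on the first dose and does not change. The gap remains for medications begun after the first dose, where SAP 9 needs a last-dose date and names no rule.

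Two stronger readings are tempting, and the documents do not support them:

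- A reader might infer that every imputed subject is credited with 8 to 14 days. Protocol 7.1.3 makes Visit 5 the early-termination visit as well, and that can fall before Day 8. Visit 5 collection is meant for subjects who discontinue, so 12-14 days is the exception. Days 10 and 11 are not scheduled visits at all.
- A reader might infer that missing dates cluster in early stoppers, so that the longest exposure goes to those who had the least. Nothing in the documents shows this. Protocol 4.4 requires the stop date on the case report form when product is discontinued, so early stoppers are the group with a mandated date.

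A last objection is that a cap could hide use beyond the regimen, which Protocol 8.1.6 may class as misuse. This is fair, and it is met by capping imputed dates only.

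**Conclusion.** The point holds at low severity. As written, 18.5 overstates duration for a completer with an unrecoverable last-dose date: by 1-2 days in the usual case (Visit 4 return) and by 5-7 days in the exceptional one (full-schedule Visit 5 return). It cannot err in the other direction. Separately, 18.5 and 18.6.2 can give the same completer two last-dose dates 3-6 days apart, and SAP 9 does not choose between them.

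The tabulated effect is confined to Table 14.3.8.1, mainly its maximum; the rest is in listings. The number of subjects affected is not given and is probably small. The conclusion rests on reading the regimen as Day 1 to Day 7 and on returns falling within the scheduled windows.

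**What to change.** In SAP 18.5, impute a last-dose date that is still missing after query as the earlier of (a) the product-return date and (b) the last planned dosing day counted from the first dose, which is Day 7 under the documents' own regimen. Apply the cap to imputed dates only, so that documented dosing beyond the regimen stays visible. Have 18.6.2 and SAP 9 refer to this one date, and flag it in Listing 16.2.5.3, as the SAP already does for imputed medication and adverse-event dates.

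A compliance-check date should not enter the rule. Protocol 6.5 has compliance verified only verbally, and taking an earlier check as the last dose could understate exposure.

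While editing, the SAP should also say what happens if product is never returned. Rule 18.5 then yields no date, although Protocol 4.4.2 foresees subjects lost to follow-up who still hold product.

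The cost is a sentence or two and two cross-references. There is one small downside: for the few imputed subjects, the cap assumes that undocumented dosing did not run past the planned regimen.

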18.6 Missing Date Information for Prior or Concomitant Medications

For prior or concomitant medications, including rescue medications, incomplete (ie, partially missing) start date and/or stop date will be imputed. When the start date and the stop date are both incomplete for a subject, impute the start date first.

18.6.1 Incomplete Start Date

The following rules will be applied to impute the missing numerical fields. If the stop date is complete and the imputed start date is after the stop date, then the start date will be imputed using the stop date.

Missing day and month

- If the year of the incomplete start date is the same as the year of the date of the first dose of investigational product, then the day and month of the date of the first dose of investigational product will be assigned to the missing fields
- If the year of the incomplete start date is before the year of the date of the first dose of investigational product, then December 31 will be assigned to the missing fields
- If the year of the incomplete start date is after the year of the date of the first dose of investigational product, then 01 January will be assigned to the missing fields.

Missing month only

- The day will be treated as missing and both month and day will be replaced according to the above procedure.

Missing day only

- If the month and year of the incomplete start date are the same as the month and year of the date of the first dose of investigational product, then the day of the date of the first dose of investigational product will be assigned to the missing day
- If either the year is before the year of the date of the first dose of investigational product or if both years are the same but the month is before the month of the date of the first dose of investigational product, then the last day of the month will be assigned to the missing day
- If either the year is after the year of the date of the first dose of investigational product or if both years are the same but the month is after the month of the date of the first dose of investigational product, then the first day of the month will be assigned to the missing day.

18.6.2 Incomplete Stop Date

The following rules will be applied to impute the missing numerical fields. If the date of the last dose of investigational product is missing, then replace it with the last visit date. If the imputed stop date is before the start date (imputed or non-imputed start date), then the imputed stop date will be equal to the start date.

Missing day and month

- If the year of the incomplete stop date is the same as the year as of the date of the last dose of investigational product, then the day and month of the date of the last dose of investigational product will be assigned to the missing fields
- If the year of the incomplete stop date is before the year of the date of the last dose of investigational product, then 31 December will be assigned to the missing fields
- If the year of the incomplete stop date is after the year of the date of the last dose of investigational product, then 01 January will be assigned to the missing fields.

Missing month only

- The day will be treated as missing and both month and day will be replaced according to the above procedure.

Missing day only

- If the month and year of the incomplete stop date are the same as the month and year of the date of the last dose of investigational product, then the day of the date of the last dose of investigational product will be assigned to the missing day
- If either the year is before the year of the date of the last dose of investigational product or if both years are the same but the month is before the month of the date of the last dose of investigational product, then the last day of the month will be assigned to the missing day
- If either the year is after the year of the last dose of investigational product or if both years are the same but the month is after the month of the date of the last dose of investigational product, then the first day of the month will be assigned to the missing day.

18.7 Missing Date Information for Adverse Events

For AEs, incomplete (i.e. partially missing) start dates will be imputed if the subject is missing whether the event occurred prior to the first study drug dose. Incomplete stop dates will not be imputed.

18.7.1 Incomplete Start Date

If incomplete start date needs to be imputed, then follow same rules as in Section 18.6.1.

18.8 Missing Severity Assessment for Adverse Events

If severity is missing for an AE starting prior to the date of the first dose of investigational product, then a severity of “Mild” will be assigned. If the severity is missing for an AE starting after the first dose of investigational product, then a severity of “Severe” will be

assigned. The imputed values for severity assessment will be used for incidence summaries, while both the actual and imputed values will be used in data listings.

18.9 Missing Relationship to Investigation Product for Adverse Events

If the relationship to investigational product is missing for an AE starting after the first dose of investigational product, a causality of “Related” will be assigned. The imputed values for relationship to double-masked investigational product will be used for incidence summaries, while both the actual and imputed values will be presented in data listings.

20. APPENDIX

20.1 Example SAS Code for Generating Descriptive Statistics

```
*For binary endpoint;  
proc freq data = testData;  
tables binary_endpoint / binomial (exact level='Yes') alpha=0.05;  
by visit treatment;  
run;
```

